Patient hands in 7 day food diary			x	x	x	x	x	x	x	x
Patient given 7 day food expenditure diary			x	x	x	x	x	x	x	x
Patient hands in 7 day food expenditure diary			x	x	x	x	x	x	x	x
End of study questionnaire										x

Statistical analysis

Outcomes will be compared between the SatPro group and patients who have followed a low calorie diet (LowCal).

Primary outcome: Change in body weight

Secondary outcomes:

Change in body composition

Change in waist to hip ratio

Change in neck circumference

Change in blood pressure

Change in glycaemic control

Change in energy expenditure

Satiety, hunger and dietary restraint

Acceptability to patients

Diet sustainability/adherence

Changes in gut and urine microbiome and metabolome

Changes in hunger and fullness gut hormones

Quantitative data will be analysed using the appropriate statistical software (GraphPad Prism and SPS) in conjunction with guidance from the Imperial College Statistical Advisory Service. Comparisons between the LowCal and SatPro groups will be performed in an intention to treat manner and sub-stratified where possible.

Qualitative data, for example free text responses in questionnaires, will be subject to thematic analysis based in Grounded Theory. Food diaries will be analysed using the appropriate software and food expenditure diaries will be analysed using the DEFRA template.

Safety and protection of patients

Clinical care

All patients, will receive multidisciplinary weight management and will progress through the standard Tier 3 pathway that is currently in operation at ICHNT.

Dietary intervention

SatPro advocates eating foods that are readily available to the general public e.g. from supermarkets and which have been subjected to governmental regulation regarding freshness, constituent ingredients etc. Adverse events (see below) related to the dietary protocol are not anticipated.

Blood sampling

Blood will be taken only by an NHS phlebotomist or by a medical practitioner or registered nurse trained in the procedure.

Withdrawal from the study

Patients will be free to withdraw at any point during the study. In addition the investigators will withdraw a patient from the study if they have identified clinical grounds for doing so.

Contact information

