Medical judgement should be exercised in deciding whether an AE is serious in other situations. Important AEs that are not immediately life-threatening or do not result in death or hospitalisation but may jeopardise the subject or may require intervention to prevent one of the other outcomes listed in the definition above, should also be considered serious.

Reporting Procedures

All adverse events should be reported. Depending on the nature of the event the reporting procedures below should be followed. Any questions concerning adverse event reporting should be directed to the Chief Investigator in the first instance.

Non serious AEs

All such events, whether expected or not, should be recorded.

Serious AEs

An SAE form should be completed and faxed to the Chief Investigator within 24 hours.

All SAEs should be reported to the Hampstead REC where in the opinion of the Chief Investigator, the event was:

- 'related', i.e. resulted from the research protocol and
- 'unexpected', i.e. an event that would not be an expected occurrence of the protocol

Reports of related and unexpected SAEs should be submitted within 15 days of the Chief Investigator becoming aware of the event, using the NRES SAE form for non-IMP studies. The Chief Investigator must also notify the Sponsor of all SAEs.

Contact details for reporting SAEs

[contact], attention of: [name]

Please send SAE forms to: Section of Investigative Medicine, Division of Diabetes, Endocrinology and Metabolism, Imperial College London

[contact] (Mon to Fr 09.00-17.00h)

Possible Adverse Events

Patients will be encouraged to report any unusual or unpleasant sensations or new symptoms to the investigator immediately. Any significant adverse effects will lead to withdrawal of the individual and any serious adverse effects will terminate the whole study.

Throughout the study there will be at least one physician available in case of a possible adverse event. Although we do not anticipate any serious adverse effects, patients will be provided with contact details and clear instructions that, if they feel unwell, they should contact us.

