It will be made clear to patients that they will be free to withdraw from the study at any time without providing any reason. Patients will be given an adverse event form to fill in and this will be reviewed at each attendance. Any possible adverse event will then be reviewed with the senior clinicians. Any significant adverse effects would lead to withdrawal of the individual and any serious adverse effects would terminate the whole trial. Any serious adverse event suspected to be related to the study would be reported to the ethics committee and the sponsor (Imperial College London).

Regulatory Issues:

Ethics approval

Ethical approvals will be sought by the Chief Investigator from Hampstead REC/HRA. The study will be conducted in accordance with the recommendations for physicians involved in research on human subjects adopted by the 18th World Medical Assembly, Helsinki 1964 and later revisions.

Consent

Consent to enter the study must be sought from each participant only after a full explanation has been given, an information leaflet offered and time allowed for consideration. The patient will have at least 24 hours after receipt of the patient information sheet to decide whether to take part. Signed participant consent should be obtained. The right of the participant to refuse to participate without giving reasons must be respected. After the participant has entered the study, the clinician remains free to give alternative treatment to that specified in the protocol at any stage if he/she feels it is in the participant's best interest, but the reasons for doing so should be recorded. In these cases the patients remain within the study for the purposes of follow up and data analysis. All patients are free to withdraw at any time from the protocol treatment without giving reasons and without prejudicing further treatment.

Loss of capacity to consent during the study

If a participant, who has given informed consent, loses capacity to consent during the study, the participant would be withdrawn from the study. Identifiable data or tissue already collected with consent would be retained and used in the study. No further data or tissue would be collected or any other research procedures carried out on or in relation to the participant. Consent for these arrangements in the event of loss of capacity will be explicitly sought in the informed consent form.

Confidentiality

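### Withdrawal on clinical grounds removes the patient from the study, and with it the weighing, which the Consent section's retention sentence does not clearly prevent

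*Combined protocol and SAP*

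**What the plan says.** Four places in the combined protocol and SAP bear on what happens to a patient who stops early.

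- **Withdrawal from the study.** After giving patients the right to leave, the section adds: "In addition the investigators will withdraw a patient from the study if they have identified clinical grounds for doing so".
- **Possible Adverse Events.** The rule appears twice: "Any significant adverse effects will lead to withdrawal of the individual", and later "Any significant adverse effects would lead to withdrawal of the individual".
- **Consent.** If it is in the participant's best interest, "the clinician remains free to give alternative treatment to that specified in the protocol at any stage", with reasons recorded. The section continues: "In these cases the patients remain within the study for the purposes of follow up and data analysis". It describes a patient's own withdrawal as leaving the protocol treatment.
- **Loss of capacity to consent during the study.** Data already held are kept and nothing further is collected.

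Under Statistical analysis, the primary outcome is change in body weight, with no time point in that line. The analysis principle is: "Comparisons between the LowCal and SatPro groups will be performed in an intention to treat manner and sub-stratified where possible". The secondary outcomes include acceptability to patients and "Diet sustainability/adherence".

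**The concern.** An intention-to-treat comparison needs outcomes from patients who stop their allocated diet as well as from those who keep to it. The clinical-grounds rule takes the patient out of the study itself and attaches no provision for later weighing. Applied literally, it ends collection of the primary outcome for a patient who might well have agreed to step on the scales.

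The reason for leaving may be related to the diet. Participants attend group sessions that support their assigned diet, so they know which one they follow, and the two diets may be tolerated differently. Weights lost for clinical or tolerability reasons could then differ between arms in number and in kind. Assigning patients to their randomised group does not supply a weight that nobody took, and the text reviewed gives no missing-data method.

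Because acceptability and adherence are outcomes too, the date and reason for stopping a diet are also results worth having in their own right.

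**Working it through.** No figure in the plan needs reproducing. The check sets the rules side by side, counts the weights at stake, and asks whether a bias can be sized.

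**1. The rules compared**

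| Route | What the patient leaves | Stated rule on later data |
|---|---|---|
| Clinical grounds (Withdrawal from the study) | The study | None |
| Significant adverse effect (Possible Adverse Events, twice) | Not specified: diet or study | None |
| Alternative treatment in the patient's best interest (Consent) | Protocol treatment | Stays in follow-up and analysis |
| Patient's own choice (Consent) | Protocol treatment | None |
| Loss of capacity | The study | Existing data kept, no more collected |

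The protocol states a data rule for alternative treatment and for loss of capacity. It states none for the first two rows.

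**2. Where the rules meet**

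- *A clinician changes a patient's care for a clinical reason and gives other dietary treatment.* The Consent sentence keeps the patient in follow-up. The clinical-grounds rule can remove the same patient. Two members of staff could act differently and each be following the protocol.
- *A patient is withdrawn on clinical grounds and given no alternative treatment.* Only the clinical-grounds rule clearly applies, and follow-up ends.
- *A patient is withdrawn for a significant adverse effect and given no alternative treatment.* The result turns on whether withdrawal means the diet or the study.

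**3. Weights at stake for one patient** (from Study Protocol, points 1 and 3 to 8)

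- Study Visits A, B and C: 3.
- Group sessions, each with a weighing: 14.
- Twice-monthly checks for five months after Visit B: 2 × 5 = 10.
- Total: 3 + 14 + 10 = about 27.

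Withdrawn after session 7: 1 + 7 = 8 weights held and 27 − 8 = 19 not collected, including Visits B and C. Withdrawn just after Visit B: 1 + 14 + 1 = 16 held and 27 − 16 = 11 not collected, including Visit C. The earlier weights survive in both cases. What is lost is everything after withdrawal, including the week 52 weight.

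**4. Can the bias be sized?**

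Suppose that only remaining patients contribute a final weight. In one arm let p be the share withdrawn, R and W the mean losses in remaining and withdrawn patients, and d = R − W. The mean over all randomised patients is (1 − p)R + pW, so the remaining-only mean exceeds it by R − [(1 − p)R + pW] = p × d. The SatPro minus LowCal difference therefore shifts by

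pS × dS − pL × dL.

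The documents give none of the four inputs. The shift is zero if the two products are equal. As a unit of scale only, 1% withdrawn in one arm and a 1 kg gap gives 0.01 × 1 = 0.01 kg. Neither the direction nor the size follows from the protocol.

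**The case against.** The strongest reply is that the protocol already leans towards retention. The Consent section keeps patients whose treatment is changed, it speaks of leaving protocol treatment and not the study, and the analysis is by intention to treat. On that view, withdrawal for an adverse effect means stopping the diet, and full removal is reserved for patients who cannot safely continue. Under Clinical care, all patients go through the standard Tier 3 pathway, which ends with an exit appointment that discusses weight, so a withdrawn patient may still be weighed in NHS care.

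Much of this stands for the adverse-effect rule, and a reader should not infer that this rule certainly ends weighing. It does not answer the clinical-grounds rule, which names the study. Nor does any sentence seen turn clinic weights taken after withdrawal into study data.

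Three stronger readings are tempting and unsupported:

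- *That the protocol flatly contradicts itself.* The Consent sentence and the clinical-grounds rule can be read as separate categories. They collide only where one reason triggers both.
- *That a withdrawn patient loses most of the outcome data.* Counting only Visits A, B and C suggests this, but it leaves out the fortnightly and twice-monthly weights. Since the primary outcome line gives no time point, a missing Visit B or C weight is not established as a missing primary endpoint.
- *That a bias of some number of kilograms follows.* Any such figure would rest wholly on assumed inputs, and on an analysis of remaining patients only, which the plan does not state.

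Reassurance should not be overread either. The Dietary intervention section says: "Adverse events (see below) related to the dietary protocol are not anticipated". That concerns events related to the diet and does not forecast how often other clinical grounds will arise.

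**Conclusion.** The point holds as a minor one. As written, withdrawal on clinical grounds ends collection of the primary outcome in a trial that promises an intention-to-treat comparison. Withdrawal for a significant adverse effect can be read the same way, but need not be. The Consent sentence reaches only patients given alternative treatment, so it does not clearly cover either group and partly overlaps with the clinical-grounds rule.

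The effect on the result is unknown in size and direction, and would be small if such withdrawals are few. The conclusion rests on the ordinary meaning of being withdrawn from a study, and on the text available. The part of the protocol between the contact information heading and the adverse-event material, and the consent pages, could not be checked and may hold a relevant sentence. This is also a self-described feasibility study, which supports treating the matter as an inexpensive improvement.

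**What to change.** Separate stopping the diet from leaving the study, and extend the Consent section's own principle to the other two rules:

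- Clinical grounds or a significant adverse effect stops the allocated diet and any study procedure judged unsafe, such as the overnight fast or blood sampling. The patient stays in the study. The investigator's judgement on what to stop is unchanged.
- Body weight is still collected at the scheduled visits, at least Visits B and C, and analysed by randomised group, unless the patient withdraws consent to follow-up or loses capacity.
- The date and reason for stopping the diet are recorded for every such patient. This is partly in place: reasons for alternative treatment and all adverse events must already be recorded.

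The cost is wording in the protocol and consent form, plus a brief weighing of each off-diet patient at visits already scheduled. The weighing does not need the fast, the blood tests or the full 3.5 hours of Visit B. Some off-diet patients will still not attend, so missing weights will be fewer but not eliminated.

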Medical judgement should be exercised in deciding whether an AE is serious in other situations. Important AEs that are not immediately life-threatening or do not result in death or hospitalisation but may jeopardise the subject or may require intervention to prevent one of the other outcomes listed in the definition above, should also be considered serious.

Reporting Procedures

All adverse events should be reported. Depending on the nature of the event the reporting procedures below should be followed. Any questions concerning adverse event reporting should be directed to the Chief Investigator in the first instance.

Non serious AEs

All such events, whether expected or not, should be recorded.

Serious AEs

An SAE form should be completed and faxed to the Chief Investigator within 24 hours.

All SAEs should be reported to the Hampstead REC where in the opinion of the Chief Investigator, the event was:

- 'related', i.e. resulted from the research protocol and
- 'unexpected', i.e. an event that would not be an expected occurrence of the protocol

Reports of related and unexpected SAEs should be submitted within 15 days of the Chief Investigator becoming aware of the event, using the NRES SAE form for non-IMP studies. The Chief Investigator must also notify the Sponsor of all SAEs.

Contact details for reporting SAEs

[contact], attention of: [name]

Please send SAE forms to: Section of Investigative Medicine, Division of Diabetes, Endocrinology and Metabolism, Imperial College London

[contact] (Mon to Fr 09.00-17.00h)

Possible Adverse Events

Patients will be encouraged to report any unusual or unpleasant sensations or new symptoms to the investigator immediately. Any significant adverse effects will lead to withdrawal of the individual and any serious adverse effects will terminate the whole study.

Throughout the study there will be at least one physician available in case of a possible adverse event. Although we do not anticipate any serious adverse effects, patients will be provided with contact details and clear instructions that, if they feel unwell, they should contact us.

It will be made clear to patients that they will be free to withdraw from the study at any time without providing any reason. Patients will be given an adverse event form to fill in and this will be reviewed at each attendance. Any possible adverse event will then be reviewed with the senior clinicians. Any significant adverse effects would lead to withdrawal of the individual and any serious adverse effects would terminate the whole trial. Any serious adverse event suspected to be related to the study would be reported to the ethics committee and the sponsor (Imperial College London).

Regulatory Issues:

Ethics approval

Ethical approvals will be sought by the Chief Investigator from Hampstead REC/HRA. The study will be conducted in accordance with the recommendations for physicians involved in research on human subjects adopted by the 18th World Medical Assembly, Helsinki 1964 and later revisions.

Consent

Consent to enter the study must be sought from each participant only after a full explanation has been given, an information leaflet offered and time allowed for consideration. The patient will have at least 24 hours after receipt of the patient information sheet to decide whether to take part. Signed participant consent should be obtained. The right of the participant to refuse to participate without giving reasons must be respected. After the participant has entered the study, the clinician remains free to give alternative treatment to that specified in the protocol at any stage if he/she feels it is in the participant's best interest, but the reasons for doing so should be recorded. In these cases the patients remain within the study for the purposes of follow up and data analysis. All patients are free to withdraw at any time from the protocol treatment without giving reasons and without prejudicing further treatment.

Loss of capacity to consent during the study

If a participant, who has given informed consent, loses capacity to consent during the study, the participant would be withdrawn from the study. Identifiable data or tissue already collected with consent would be retained and used in the study. No further data or tissue would be collected or any other research procedures carried out on or in relation to the participant. Consent for these arrangements in the event of loss of capacity will be explicitly sought in the informed consent form.

Confidentiality

The Chief Investigator will preserve the confidentiality of patients taking part in the study. The confidentiality of NHS records pertaining to study patients will be maintained as set out in the NHS Confidentiality Policy 2014 (<http://www.england.nhs.uk/wp-content/uploads/2013/06/conf-policy-1.pdf>).

Patient identifiable data will only be accessible to members of the direct care team. Researchers named in this application who are not members of the direct care team will only have accessed to anonymised data. A single computer file with all personal data will be kept on a password protected Imperial College Healthcare NHS Trust (ICHNT) computer. Only data which has been anonymised will be analysed within Imperial College London.

Indemnity

Imperial College London holds negligent harm and non-negligent harm insurance policies which apply to this study.

Funding

[name] is the recipient of BRC Funding Support for NIHR Academic Trainees. The IWC weight management programme (Tier 3) service will be funded as per previous NHS funding arrangements.

Audits

The study may be subject to inspection and audit by Imperial College London under their remit as sponsor and other regulatory bodies to ensure adherence to GCP and the NHS Research Governance Framework for Health and Social Care (2nd edition).

Study Management

The day-to day management of the study will be co-ordinated through [name] and [name] with assistance from those named ICHNT medically qualified personnel as well as allied health professionals working within the Imperial Weight Centre, ICHNT. A data monitoring committee comprising the trial investigators as well as an external assessor will meet on a quarterly basis. The results of the study will be shared with the participants. The study will be published in peer review scientific journals.

References:

1. N Engl J Med (1995) 332:621;
2. N Engl J Med (2011) 365:1597
3. Obesity (Silver Spring). 2016 May 2. doi: 10.1002/oby.21538. [Epub ahead of print]
4. Cell Metab (2006) 4:223
5. N Engl J Med (2010) 363(22):2102-13
6. Diabetes (1965) 14:549
7. Nat Rev Endocrinol 10:540
8. N Engl J Med (2008) 359:229
9. N Engl J Med (2014) 368:1279
